5 CRITERIA FOR EVALUATION

5.1 Primary Efficacy Endpoint

We used FEV1 measures from 219 adults with asthma published in Corren et al. NEJM, 2011¹. The authors found that the standard deviation for the change in FEV1 in liters from day 1 to day 7 was 19%. Using a standard deviation of 19 and a two-sided alpha of 0.05, we calculate a sample size of 30 to have 80% power to detect a change in FEV1 of 10% (a reasonable effect size because early studies of Pulmozyme in CF reported a 10% increase in FEV1 at day 3 of treatment)⁷.

5.2 Secondary Efficacy Endpoints

We intend to examine the effect of the treatment on CT mucus score in a subset of participants. Because the CT mucus score is a novel measurement, we do not have preliminary data to describe the natural history of mucus in the airway over time or with treatment. Therefore, for the purpose of this study, we intend to describe any changes we observe.

With respect to drug tolerability, we will first analyze the two treatment periods to assess any negligible carryover effects and then describe frequencies of reported side effects.

5.3 Safety Evaluations

All participants will have their first dose of treatment or normal saline administered in the clinical laboratory environment under the supervision of a study nurse or study clinician. Participants will receive instruction on nebulizer use utilizing a teach-back method to ensure comprehension. Participants who are unable to successfully teach back nebulizer setup or drug self-administration will be excluded from continued participation.

Additionally, while acute anaphylactoid reactions have only been observed in the setting of IV administered NAC, each participant will be observed for 30 minutes following initiation of each new study period by a study nurse or study clinician.

All participants will be asked to complete a log of study drug administration, concomitant medications, and any subjective side effects (appendix A). Additionally, participants will have access via pager to a study nurse or clinician 24 hours a day, 7 days a week.

Interim safety evaluations will be triggered if anticipated adverse events exceed frequencies documented in the literature, unanticipated adverse events occur, or rare but serious adverse events occur. Definitions of these terms and details of our safety evaluation plan are described in section 14.

6 PARTICIPANT SELECTION

6.1 Study Population

Participants with a diagnosis of asthma who meet the inclusion and exclusion criteria will be eligible for participation in this study.

Version #:1.5 Version Date: 8/5/2016 Page 15 of 41

6.2 Inclusion Criteria

- 1. Male or female between the ages of 18 and 70 years of age at Visit 0.
- 2. Able to perform reproducible spirometry according to ATS criteria
- 3. Clinical history consistent with moderate to severe asthma for 1 year or greater.
- 4. Post-bronchodilator FEV1 <90% of predicted
- 5. Prescription and daily use of inhaled corticosteroid (ICS) equivalent to 80mcg of beclomethasone or greater
- 6. CT mucus score >3 (determined during the initial screening process, provided the prior two conditions are met)
- 7. Written informed consent obtained from participant and ability for participant to comply with the requirements of the study.

6.3 Exclusion Criteria

- 1. Pregnant, breastfeeding, or unwilling to practice birth control during participation in the study.
- 2. Presence of a condition or abnormality that in the opinion of the Investigator would compromise the safety of the patient or the quality of the data.
- 3. History of intolerance to study medications.
- 4. Current use of carbamazepine
- 5. Angina which includes a treatment plan with PRN nitroglycerin or nitrites
- 6. Smoking of tobacco or other recreational inhalants in last year and/or >10 pack-year smoking history
- 7. Current participation in an investigational drug trial
- 8. Other chronic pulmonary disorders, including (but not limited to) cystic fibrosis, chronic obstructive pulmonary disease, chronic bronchitis, vocal cord dysfunction (that is the sole cause of respiratory symptoms and at the PI's discretion), severe scoliosis or chest wall deformities that affect lung function, or congenital disorders of the lungs or airways.

All participants should be maintained on the same medications throughout the entire study period, as medically feasible, with no introduction of new chronic therapies.

6.4 Allowed Medications and Treatments

Standard therapy for asthma is allowed except for treatments noted in the exclusion criteria described above and as noted in the prohibited medications section below.

Prohibited Medications and Treatments

The following medications are prohibited during the study and administration will be considered a protocol violation.

- Thiols and thiol derivatives
- Carbamazepine
- Nitroglycern and nitrates

7 STUDY TREATMENTS

7.1 Method of Assigning Participants to Treatment Groups

Up to 30 eligible patients will be randomly assigned to receive either the experimental treatment (20% NAC) or the placebo treatment (0.9% saline) during period 1 in a 1:1 ratio using a SAS-based computer-generated randomization scheme developed by the study data manager. The investigational pharmacy, who will supply the prepared study medication packets, will complete a randomization worksheet at the end of run-in and log group assignment. This log will be shared with investigators upon study completion or in the event of a serious safety concern.

7.2 Blinding

Due to the objectives of the study, the identity of experimental and placebo treatments will not be known to investigators, research staff, or patients. The following study procedures will be in place to ensure double-blind administration of study treatments.

Access to the randomization code will be strictly controlled.

Packaging and labeling of experimental and placebo treatments will be identical to maintain the blind.

The study blind will be broken on completion of the clinical study and after the study database has been locked.

During the study, the blind may be broken **only** in emergencies when knowledge of the patient's treatment group is necessary for further patient management. When possible, the Investigator should discuss the emergency with a Quality Assurance officer and a representative from the Committee on Human Research prior to unblinding. Should unblinding become necessary the Investigator will contact the investigational pharmacist directly.

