4 STUDY DESIGN

4.1 Study Overview

This is a single center, double-blind, randomized, 2 period crossover trial. We propose a sample size of 30. Following a five-day run-in period, during which participants will self-administer 0.9% normal saline by nebulizer three times per day, each participant will be randomized to receive a nebulized dose of study drug three times per day for seven days of either 20% NAC (active) or 0.9% saline (placebo). Following a 28-day washout period, participants will be switched to the alternate group for 7 days of treatment. Participants will be assigned to the treatments in random order. Evaluations will be taken at baseline, end of run-in, start of second treatment period, and at the end of each 7-day treatment period.

Screening data will be reviewed to determine participant eligibility. Participants who meet all inclusion criteria and none of the exclusion criteria will be entered into the study.

The following treatment regimens will be used:

- Experimental treatment of NAC 20%
- Placebo treatment of 0.9% saline

Total duration of participation will be nine weeks. Total duration of the study is expected to be 2 years.

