7.4.1 Dosage/Dosage Regimen

During each treatment period (see Appendix B), participants will nebulize one vial of study drug using a tabletop nebulizer. Participants will be instructed to take three doses per day, spaced at approximately 6-8 hour intervals. No adjustments will be made based weight or age. Because NAC can cause transient lung irritation, participants will be instructed to take 2 puffs of supplied albuterol 15 minutes prior to each study treatment.

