9.5 Visit 5 (Day 14)

- 1. Record any adverse experiences and/or review participant diary for adverse experiences and exclusionary medication use.
- 2. Record changes to concomitant medications.
- 3. Perform abbreviated physical examination.
- 4. Perform and record vital signs.
- 5. Perform and record oximetry.
- 6. Perform and record spirometry.
- 7. Perform and record post-bronchodilator spirometry.
- 8. Collect any unused study drug.
- 9. Review diary card.
- 10. Obtain a CT scan of the thorax.
- 11. Collect induced sputum.
- 12. Schedule participant for Visit 6 in 14 days.

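### Section 7.2 protects only the code and the packaging, so treatment may be guessed by participants or staff before the primary FEV1 is measured at Visits 5 and 8

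*Combined protocol and SAP*

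**What the plan says.** Section 7.2 sets the aim that "the identity of experimental and placebo treatments will not be known to investigators, research staff, or patients". Two of its measures act against a guess: "Access to the randomization code will be strictly controlled", and "Packaging and labeling of experimental and placebo treatments will be identical to maintain the blind". The rest of the section concerns when and how the blind is broken. Section 7.1 adds that the pharmacy holds the assignment log until study completion or a serious safety concern.

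Section 4.1 describes the lead-in: "Following a five-day run-in period, during which participants will self-administer 0.9% normal saline by nebulizer three times per day". The same section lists the comparator as "Placebo treatment of 0.9% saline". Visit 4 (section 9.4) ends the run-in, requires at least 80% adherence, randomises, and gives the first study dose under nurse or physician supervision.

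On the active product, section 7.4.1 says "Because NAC can cause transient lung irritation, participants will be instructed to take 2 puffs of supplied albuterol", to be taken before each study treatment. Section 2.1 reports nausea in 2-7% and vomiting in 9-12% of cases, and lists cough without a rate. Table 1 in 7.3.1 gives different ingredients and pH (7 for NAC, 5.7 for saline).

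Item 1 of the Visit 5 list (9.5), repeated at Visit 8 (9.8), is "Record any adverse experiences and/or review participant diary for adverse experiences and exclusionary medication use". In both lists spirometry is item 6, post-bronchodilator spirometry item 7, and a further diary-card review item 9.

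**The concern.** Identical packages and a locked code stop anyone from reading the allocation. They do not stop anyone from inferring it from the product. Three features make an inference plausible here. The run-in gives each participant a recent reference for what saline is like. NAC has effects that a participant may feel and a diary may record. In a two-period crossover, a correct guess in one period also reveals the other.

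The primary outcome is the percentage change in FEV1 over each period. FEV1 depends on the participant's effort and the operator's coaching, so either person's expectation could enter the NAC-placebo contrast. The plan does not say that spirometry comes before symptom review, and it does not keep the person who watched the first dose or read the diary away from the spirometer. It plans no check of blinding, so a reader of the results would have no information on whether the blind held.

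**Working it through.** **1. Run-in exposure (4.1, 9.4).** 5 days x 3 doses = 15 doses of 0.9% saline. The 80% adherence rule gives 0.80 x 15 = 12 as the minimum. The ±5-day visit window could change the count, so *about 15* is the right description. The first randomised dose follows at the visit that ends the run-in.

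**2. Order of procedures (9.5, 9.8).**

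| Item | Visits 5 and 8 |
|---|---|
| 1 | Adverse events and/or diary |
| 2-5 | Concomitant medication, abbreviated examination, vital signs, oximetry |
| 6-7 | Spirometry, then post-bronchodilator spirometry |
| 9 | Diary card |

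The diary (Appendix A) logs wheeze, cough, chest tightness, shortness of breath and other symptoms dose by dose.

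**3. How many participants nausea or vomiting might mark (2.1).** Treat each reported rate as a rate per NAC period.
- If independent: 1 - (0.98 x 0.91) = 10.8%, up to 1 - (0.93 x 0.88) = 18.2%.
- If never in the same person: 2 + 9 = 11%, up to 7 + 12 = 19%.
- Of 30 participants: about 3 to 6.

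Irritation and cough have no stated rate and cannot be added.

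**4. The plan's own sample size (14.6).** Inputs: SD 19, difference 10, two-sided alpha 0.05, power 80%. For a paired comparison, n = ((1.96 + 0.84) x 19/10)² = 28.3, rounded up to 29. Exact noncentral-t power at n = 30 is 79.6%. The stated 30 is reproduced if 19 is the SD of the within-person NAC-placebo difference.

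**5. Illustration of scale; the bias sizes are assumed.** SE = 19/√30 = 3.47 points. Suppose there is no true effect and guessing shifts the mean difference by b points. The chance of p < 0.05 is the noncentral-t rejection probability with 29 degrees of freedom and noncentrality b/SE.

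The documents give 19 as the SD of a change over one period. If it is that, and r is the within-person correlation of the two periods' changes, the SD of the difference is 19 x √(2(1 - r)). This is 19 at r = 0.5 and 26.9 at r = 0, where SE = 26.9/√30 = 4.91.

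| Assumed bias (points) | SD 19 | SD 26.9 |
|---|---|---|
| 0 | 5% | 5% |
| 2 | 8.6% | 7% |
| 3 | 13.3% | 9% |
| 5 | 28.6% | 17% |

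**6. What those biases would require.** If only the 3 to 6 participants in step 3 were unmasked, a mean bias of 3 points would need 3 x 30/6 = 15 to 3 x 30/3 = 30 points in each of them. A mean bias of 5 would need 25 to 50. Biases of this size are therefore credible only if guessing is much more widespread, for instance through irritation or the feel of the product, on which the documents give no figure.

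**The case against.** The strongest reply is that nothing shows the solutions can be told apart. NAC is described as colourless, and both products come in single-use rubber-topped glass vials. No section says that they differ in taste or smell, or that participants are told the run-in is saline. A reader might infer that the blind will fail; the documents do not support that. They support only a risk, resting on stated irritant and gastrointestinal effects and recent familiarity with saline.

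A reader might also infer that staff must read the diary before spirometry. The lists are not declared a fixed sequence, item 1 reads and/or, and diary review recurs at item 9. What stands is that item 1 comes first and nothing requires spirometry to precede it.

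Partial safeguards exist. Albuterol before every dose of either product may blunt the irritation cue. Dosing is supervised by a nurse or physician, while section 8.1.9 mentions coordinators at spirometry. Spirometry follows American Thoracic Society standards. The named diary symptoms are also symptoms of the asthma under study. These lower the risk, but none is a rule separating the roles.

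The direction of bias is open too: an irritating product could lower expectation and work against NAC.

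**Conclusion.** The point holds as a gap in the protection of the blind. Section 7.2 covers only the code and the package, and the end-of-period visits leave open a route by which staff may form a guess before the primary measure. Participants may form one from the product itself. Neither is shown to happen.

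The size is unknown. The figures of 9%, 13% and 29% (7%, 9% and 17% at the larger SD) depend on assumed biases of 2, 3 and 5 points in NAC's favour and on how SD 19 is read. They should not be taken as the trial's expected false-positive rate. The sample size is not in question on this point. The case for acting is that the staff route can be narrowed cheaply and without losing data, because diary review is already listed again after spirometry.

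**What to change.** - **9.5 and 9.8:** state that spirometry and post-bronchodilator spirometry come before the detailed adverse-event and symptom-diary review. Keep vital signs, oximetry, physical examination and the concomitant-medication check first. Leave any safety check needed before spirometry to clinical staff who do not run the test.
- **7.2:** state that, within the existing team, whoever supervises dosing at Visits 4 and 7 or reviews the diary does not run spirometry at Visits 5 and 8.
- **Treatment guesses, if recorded:** take them from participant and operator before FEV1 results are known, preferably from participants only at Visit 8 so that the question does not affect period 2. Report them descriptively. Do not split the primary estimate by guess: a guess is made after randomisation and may itself reflect improvement, so the subgroup estimates would be confounded.

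The cost is visit order, a rota rule and minor scheduling friction. Dose, schedule, eligibility and sample size do not change. These steps limit bias from staff; they do not remove guessing by participants, who know their own symptoms.

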7.3 Formulation of Test and Control Products

NAC (trade name: Mucomyst) is manufactured by American Regent. The active drug studied here is 20% NAC delivered via nebulizer. The placebo is 0.9% saline. Both solutions will be delivered by the Sponsor's compounding pharmacy in single-use rubbertopped glass vials.

7.3.1 Formulation of Test Product

20% NAC is an existing formulation of Mucomyst (Mucomyst-20), manufactured by American Regent, for aerosol administration in the management of patients with chronic bronchopulmonary disease. 20% NAC is a colorless solution that requires no reconstitution.

Table 1: Formulation and Measured pH of 20% NAC and Control Product

	20% NAC	0.9% Saline
Active Ingredient, mg/mL	Acetylcysteine 200mg/mL	
Other ingredient	Edetate disodium	Sodium chloride
	Sodium hydroxide	Purified water
	Purified water	
рН	7	5.7

7.3.2 Formulation of Control Product

A placebo solution of 0.9% saline will be prepared by the UCSF Drug Products Services Laboratory in single-use rubber-topped glass vials.

7.3.3 Packaging and Labeling

Study drug is supplied in a package containing 24 single-use rubber-topped glass vials (3 extra vials in the event of breakage).

Each package of study drug will be labeled with the required FDA warning statement, the protocol number, a treatment number, the name of the sponsors, and directions for patient use and storage.

7.4 Supply of Study Drug at the Site

The UCSF Drug Products Services Laboratory will prepare Study Drug and deliver it to the Airway Clinical Research Center. Study drug kits will be delivered upon successful completion of the run-in period on an individual participant basis.

7.4.1 Dosage/Dosage Regimen

During each treatment period (see Appendix B), participants will nebulize one vial of study drug using a tabletop nebulizer. Participants will be instructed to take three doses per day, spaced at approximately 6-8 hour intervals. No adjustments will be made based weight or age. Because NAC can cause transient lung irritation, participants will be instructed to take 2 puffs of supplied albuterol 15 minutes prior to each study treatment.

7.4.2 Dispensing

Study medication will be dispensed by either a study nurse or physician and only after direct observation of the administration of the first dose of each treatment period.

7.4.3 Administration Instructions

Nebulizer and Air Compressor Assembly

- a. Place the compressor on a clean flat surface where it can safely reach its power source and where the ON/OFF switch can be reached.
- b. Wash hands prior to preparing each treatment.
- c. Use a clean nebulizer.

- d. Inspect your nebulizer and ensure that the green exhalation valve on the mouthpiece is pointing down.
- e. Connect one end of the tubing to the bottom of the nebulizer and the other end to the air outlet on the compressor. Ensure that both ends are securely attached.
- f. Make sure the nebulizer top is in breath actuated mode.
- g. Remove one vial of study drug from refrigerator and carefully add to the nebulizer.

Prior to Beginning Study Drug Treatment

a. Take 2 puffs of the albuterol inhaler (provided by study) 15 minutes before starting treatment.

Beginning Study Drug Treatment

- a. Place the mouthpiece in your mouth, making sure your lips are sealed around the edge but are not covering the exhalation valve.
- b. Hold the nebulizer in an upright position. This prevents spilling and promotes nebulization.
- c. Breathe in slowly and deeply and then exhale normally through the device.
- d. Occasionally tapping the side of the nebulizer helps the solution drop to where it can be misted.
- e. Continue taking slow, deep breaths until the noise created by the device changes—this sound is sometimes referred to as a 'sputter'.
- f. Switch off compressor when finished with treatment.

Care and Cleaning of Nebulizer Equipment after Each Use

- a. Wash hands.
- b. Remove tubing from nebulizer.
- c. Open nebulizer cup and shake out any remaining liquid.
- d. Empty the supplied saline bullet into the nebulizer cup. Swirl in cup and empty out excess.
- e. Remove nebulizer top and mouthpiece from the nebulizer cup.
- f. Shake the nebulizer parts to remove excess liquid.
- g. Thoroughly air dry parts on drying rack before reassembling.

Care and Cleaning of Nebulizer Equipment Every Other Treatment Day

- a. Wash hands.
- b. Take the nebulizer apart.
- c. Put all of the parts, except tubing and compressor, in boiling water for 10 minutes.
- d. After boiling the nebulizer shake off any excess water, taking care not to burn skin.
- e. Thoroughly air dry parts on drying rack before reassembling.

7.5 Supply of Study Drug at the Site

Study drug supply will be maintained by the UCSF Investigational Pharmacy and will be supplied on a per participant basis. 7-day study drug supplies will be delivered to the clinical laboratory within 1 hour of study visit corresponding to the start of each treatment

Version #:1.5 Version Date: 8/5/2016 Page 19 of 41

period. Replacement kits will be available for up to 8 participants, should replacement participants be needed in order to obtain the final enrolled cohort of 30 participants.

7.5.1 Storage

Study drug should be stored by the study site at controlled room temperature, 15 to 30°C (59 to 86°F). If the temperature of study drug storage in the clinic/pharmacy exceeds or falls below this range, this should be reported to the Sponsor or designee and captured as a deviation. Participants will be instructed to store the medication in original packaging at room temperature according to the instructions outlined on the Drug Administration Instructions.

7.6 Study Drug Accountability

An accurate and current accounting of the dispensing and return of study drug for each participant will be maintained on an ongoing basis by a member of the study site staff. The number of study drug dispensed and returned by the participant will be recorded on the Investigational Drug Accountability Record. The study monitor will verify these documents throughout the course of the study.

7.7 Measures of Treatment Compliance

Participants will be asked to keep a patient diary noting the day and date they take their study drug and any adverse events. They will be asked to bring their patient diary to each study visit along with all used and unused study drug containers (Appendix A).

8 STUDY PROCEDURES AND GUIDELINES

A Schedule of Events representing the required testing procedures to be performed for the duration of the study is diagrammed in Appendix B.

Prior to conducting any study-related activities, written informed consent and the Health Insurance Portability and Accountability Act (HIPAA) authorization must be signed and dated by the participant.

